## Embryo/fetal exposure

Embryo/fetal exposure to study drug by sponsor was calculated from the conception date by site/sponsor to the date of maternal last dose of study drug.

# 10.0 Overall Type-I Error Control

The objective of this study is to evaluate the long-term safety and tolerability of elagolix 300 mg BID with E2/NETA. No primary or secondary efficacy endpoint is defined.

Since the End of 12-Month Placebo-Controlled Treatment Period analysis is the only and final analysis for the comparison between treatment and placebo group at 12 months of safety and efficacy endpoints, no additional adjustment of alpha-level is necessary.

# 11.0 Version History

## Table 1.SAP Version History Summary

Version	Date	Summary
1.0	20 January 2021	Original version

# Appendix A.Definition of Adverse Events of Special Interest (AESI) Adverse
Events of Special Interest

Item of Safety Interest	Method of Surveillance
Hot flashes/night sweats	Non-bone related hypoestrogenic effects CMQ
Bone mineral density loss	Osteoporosis/Osteopenia SMQ
	DXA results from clinical trials
Anemia	Cases are identified through the Non-Hemolytic and Non-Aplastic Anemias CMQ
	Haematopoietic erythropenia SMQ
Bone Fractures	Osteoporosis/osteopenia SMQ Bone fracture CMQ
Rash and hypersensitivity reactions	Anaphylactic reaction SMQ
	Severe cutaneous adverse reactions SMQ
	Drug induced rash CMQ
Lipid abnormalities	Dyslipidemia SMQ
Uterine bleeding change	Female reproductive bleeds CMQ
Endometrial safety	Uterine and fallopian tube neoplasms, malignant and unspecified SMQ
	Reproductive Premalignant Disorders SMQ
	Endometrial biopsy results
Hypoestrogenic AEs (excluding hot flashes, BMD loss, and fractures)	Non-bone related hypoestrogenic effects CMQ
Spontaneous abortion	Termination of pregnancy and risk of abortion SMQ
Teratogenicity	Review of pregnancy outcome
	All pregnancies will be followed up to 6 to 12 months post-delivery and reviewed at least quarterly and as they occur
Obstetrical complications (maternal and infant)	Pregnancy, labor, and delivery complications and risk factors (excluding abortions and stillbirths) SMQ
Psychiatric events	Depression and suicide/self-injury SMQ
Cardiovascular events	Cardiac arrhythmias SMQ, Cardiomyopathy SMQ,
	and Ischemic heart disease SMQ
Thromboembolic events	Embolic and thrombotic events SMQ
Alopecia	Alopecia, diffuse alopecia, androgenic alopecia
Hepatic events	Drug related hepatic disorders comprehensive SMQ, Enhanced pharmacovigilance hepatic terms PMQ
Hormonally mediated malignancies	Breast neoplasms, malignant and unspecified SMQ
	Uterine and fallopian tube neoplasms, malignant and unspecified SMQ
	Ovarian neoplasms, malignant and unspecified SMQ

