#### 8.1.7.2 Adverse Events

Unless otherwise specified, all summaries/analyses involving AEs will only include treatment-emergent adverse events (TEAEs). TEAEs are defined as any AE with an onset or increased severity after the first dose of study drug and no more than 30 days after the last dose date of study drug. AEs where the onset date is the same as the first dose date of study drug are assumed to be treatment-emergent, unless the first dose time of study drug and the AE start time are collected and the AE start time is prior to the first dose time of study drug. If an incomplete onset date was collected for an AE, the AE will be assumed to be treatment-emergent unless there is evidence that confirms that the AE was not treatment-emergent (e.g., the AE end date was prior to the first dose date of study drug).

AEs starting more than 30 days following discontinuation of the study drug will not be included in the summaries of TEAEs.

TEAEs will be coded using the Medical Dictionary for Regulatory Activities (MedDRA) version 19.0 or higher. TEAEs will be summarized using MedDRA system organ classes (SOCs) and preferred terms (PTs) and grouped by treatment group.

For each TEAE summary, the number and percentage of subjects experiencing at least one TEAE will be presented. Subjects reporting more than one TEAE within a SOC will be counted only once for that SOC. Subjects reporting more than one TEAE for a PT will be counted only once for that PT.

When summarizing TEAEs by relationship or severity, if a subject has an event with unknown severity or relationship, then the subject will be counted in the severity/relationship category of "unknown," even if the subject has a second occurrence of the same event with a severity/relationship present. The only exception is if the subject has a second occurrence of the same event with the most extreme severity (i.e., "severe") or a relationship category of "reasonable possibility." In this case, the subject will be counted under these most extreme severity/relationship categories.

Frequencies and percentages of subjects with TEAEs will be calculated for each treatment group as follows:

- Any TEAE
- Any TEAE reasonably possibly related to study drug
- Any TEAE leading to discontinuation of study drug
- Any treatment-emergent serious AE (SAE)
- Any SAE reasonably related to study drug
- Any AESI (e.g., hypoestrogenic adverse events)

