# TEAEs during the open-label Treatment Period on the Safety Analysis Set during the open-label Treatment Period

TEAEs during the open-label Treatment Period are defined as any AEs with the onset that is on or after the first dose of study drug during the open-label Treatment Period and no

more than 30 days after the last dose of study drug in the study. AEs starting more than 30 days following discontinuation of study drug will not be included in summaries of treatment-emergent AEs but will be summarized separately.

TEAEs for All Elagolix plus E2/NETA Analysis Set

TEAEs for All Elagolix plus E2/NETA Analysis Set are defined as any AEs with the onset that is on or after the first dose of elagolix plus E2/NETA (either in the placebocontrolled Treatment Period or open-label Treatment Period) and no more than 30 days after last dose of elagolix plus E2/NETA. AEs starting more than 30 days following discontinuation of study drug will not be included in summaries of treatment-emergent AEs but will be summarized separately.

The number and percentage of subjects experiencing treatment-emergent AEs will be summarized overall, as well as by primary MedDRA SOC and PT by treatment group. The SOCs will be presented in alphabetical order, and the PTs will be presented in alphabetical order within each SOC.

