## 9.2.6 Adverse Events of Special Interest

Adverse events of special interest will be summarized by SOC and PT and will be based on standardized or company MedDRA queries (SMQs or CMQs), or based on adjudication results.

Detailed information about the search criteria are provided in Appendix A.

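### Does giving both hypoestrogenic rows of SAP Appendix A the same query make the special-interest tables contradict their labels?

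*SAP*

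**What the plan says.** SAP 9.2.6 states that "Adverse events of special interest will be summarized by SOC and PT", using standardized or company MedDRA queries or adjudication results, and adds: "Detailed information about the search criteria are provided in Appendix A".

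Appendix A is a two-column table, with the item of interest on the left and the method of surveillance on the right. Two of its rows concern us. One is for hot flashes and night sweats; the other is labelled "Hypoestrogenic AEs (excluding hot flashes, BMD loss, and fractures". Both have the same single entry on the right, "Non-bone related hypoestrogenic effects CMQ". Neither row lists preferred terms, and no other section does so for them. The alopecia row does name terms: "Alopecia, diffuse alopecia, androgenic alopecia". The bone fracture row reads "Osteoporosis/osteopenia SMQ Bone fracture CMQ", and the first of those two queries is also used for bone mineral density loss.

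On totals, protocol 8.1.7.2 says: "For each TEAE summary, the number and percentage of subjects experiencing at least one TEAE will be presented". SAP 9.2.1 says that women "experiencing treatment-emergent AEs will be summarized overall, as well as by primary MedDRA SOC and PT by treatment group". The overview in SAP 9.2.2 has one line for any event of special interest, taken over the whole of Appendix A.

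**The concern.** One query yields one set of events. If that set is reported under a label for hot flashes and again under a label that excludes them, the two rows show the same women and cannot both be right. Safety is the study's purpose, and protocol 8.1.7.2 uses hypoestrogenic events as its example of an event of special interest. The protocol's benefit-risk section also relies on add-back therapy reducing hot flushes. A row that claims to leave hot flushes out, while its total and system organ class subtotals include them, would misstate the remaining hypoestrogenic burden. Because hot flush is expected more often on elagolix, it would do so unequally between arms.

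The fracture row raises a similar question. If its two queries are pooled, events that are not fractures might be counted as fractures.

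**Working it through.** The plan gives no figure to reproduce here. The check has three parts.

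**1. The rows read literally.** Let S be the terms in the shared query and H the hot flash terms.
- S holds H and other terms: both labels fail.
- S holds H only: the excluding row fails.
- S holds no H: the hot flash row fails.

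No content of S satisfies both labels if S is used whole in both rows.

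**2. The rows read with their labels.** Let N be the night sweat terms. The first row is then S ∩ (H ∪ N) and the second is S \ H. Protocol 6.1.1.3 names hot flashes together with the other non-bone hypoestrogenic events, which fits one query that covers both items. The only open question is whether N appears in the first row alone or in both.

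The overview line is a union over rows. Used whole, S ∪ S = S. Split by label, [S ∩ (H ∪ N)] ∪ (S \ H) = S. It does not change. Each preferred-term line counts the women with that term, so it does not change either. SAP 9.2.3 also lists every treatment-emergent event by preferred term, sorted by frequency in the elagolix group, so hot flush is visible there regardless.

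**3. Size if the query were applied unfiltered.** Inputs: hot flush rates of 10.8% on this regimen and 3.1% on placebo (protocol 3.2.2, Phase 2b Cohort 1, a six-month study), and arm sizes of 333 and 167 (SAP 2.4).
- Elagolix: 333 × 0.108 = 36.0
- Placebo: 167 × 0.031 = 5.2

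With the protocol's 335 and 165, the results are 36.2 and 5.1. The percentages fit 7/65 and 2/65, where the denominators are inferred from the serious adverse event percentages in the same section. Exact 95% intervals of 4.4–20.9% and 0.4–10.7% give 15–70 elagolix and 1–18 placebo women. If twelve-month rates were 1.5 times the six-month rates (an assumption), the counts would be about 54 and 8.

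These are upper bounds on misplacement, because a woman with hot flush and another hypoestrogenic event belongs in the second row anyway. If other hypoestrogenic events had the same rate q in both arms, independently of hot flush (an assumption), the unfiltered row would show an arm difference of (1 − q) × (0.108 − 0.031). That is 7.3 percentage points at q = 0.05 and 6.2 at q = 0.20.

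The fracture row cannot be sized, because the contents of its queries are not in the documents.

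**The case for a change.** The best case for a change runs as follows. Appendix A is where the SAP places its search criteria, and a label is not a search criterion. The alopecia row shows that terms are listed when a term-level definition is meant. The labels do not divide the query cleanly either: the first covers night sweats while the second excludes only hot flashes, so two programmers could build different tables. The general rules in protocol 8.1.7.2 and SAP 9.2.1 call for subject totals, where an error would show. A short term list would cost almost nothing.

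Part of this stands. The query is duplicated, the term list is absent, and the place of night sweats is unstated.

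The rest is weaker. The alopecia row lists terms in place of a query, not to cut one down, so it sets no precedent for these rows. A total for each Appendix A item is an inference. SAP 9.2.6 asks for system organ class and preferred term, and 9.2.2 asks for one overall line. Entries such as DXA results, biopsy results and review of pregnancy outcomes show that the appendix is a surveillance list, not a set of table layouts, so one table from the shared query could serve both items. Taking night sweats out of the second row would also alter a definition whose label does not exclude them.

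On the fracture row, several items list more than one query, and protocol Appendix C itself groups the bone events, so overlap is no error.

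**Conclusion.** No amendment is needed. The second label states what to leave out, and an analyst building the term lists would apply it. This is missing detail that is sensibly filled at programming, when the lists must in any case be matched to the MedDRA version in use at lock (SAP 9.2).

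A misleading row needs three things together: item-level totals are produced, the query contains hot flush terms, and it is run without regard to the label. The distortion would then be at most about 36 elagolix and 5 placebo women, provided six-month Phase 2b rates carry over to the twelve-month period. The hot flush lines in the same output would show the reader where they came from.

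The adverse event sections of the SAP attach no test to these items. Protocol 8.1.7.1 has a general provision for chi-square or Fisher tests on categorical safety data; if it were used on an item total, the same three conditions would apply. Neither study objective turns on how this one query is divided.

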#### 6.1.1.2 Serious Adverse Events

If an adverse event meets any of the following criteria, it is to be reported to AbbVie as a serious adverse event (SAE) within 24 hours of the site being made aware of the serious adverse event.

**Life-Threatening** An event that, in the opinion of the investigator, would

have resulted in immediate fatality if medical intervention had not been taken. This does not include an event that would have been fatal if it had occurred in a more severe

form.

Hospitalization or Prolongation of Hospitalization An event that results in an admission to the hospital for any length of time or prolongs the subject's hospital stay.

This does not include an emergency room visit or

admission to an outpatient facility.

**Congenital Anomaly** An anomaly detected at or after birth, or any anomaly that

results in fetal loss.

Persistent or Significant Disability/Incapacity

An event that results in a condition that substantially interferes with the activities of daily living of a study subject. Disability is not intended to include experiences of relatively minor medical significance such as headache, nausea, vomiting, diarrhea, influenza, and accidental

trauma (e.g., sprained ankle).

Important Medical
Event Requiring
Medical or Surgical
Intervention to Prevent
Serious Outcome

An important medical event that may not be immediately life-threatening or result in death or hospitalization, but based on medical judgment may jeopardize the subject and may require medical or surgical intervention to prevent any of the outcomes listed above (i.e., death of subject, life-threatening, hospitalization, prolongation of hospitalization, congenital anomaly, or persistent or significant disability/incapacity). Additionally, any elective or spontaneous abortion or stillbirth is considered an important medical event. Examples of such events include allergic bronchospasm requiring intensive treatment in an emergency room or at home, blood dyscrasias or convulsions that do not result in inpatient hospitalization, or the development of drug dependency or drug abuse.

[figure not shown]
For serious adverse events with the outcome of death, the date and cause of death will be recorded on the appropriate case report form.

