Pregnancy in a study subject is not considered an adverse event. However, the medical outcome for mother or infant, meeting any serious criteria including an elective or spontaneous abortion, stillbirth or congenital anomaly is considered a serious adverse event and must be reported to AbbVie within 24 hours of the site becoming aware of the event.

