## 9.2.2 Adverse Event Overview

An overview of treatment-emergent AEs will be presented consisting of the number and percentage of subjects experiencing at least one event for each of the following AE categories:

- Any treatment-emergent AE
- Any treatment-emergent AE related to study drug according to the investigator
- Any severe treatment-emergent AE
- Any serious treatment-emergent AE
- Any treatment-emergent AE leading to discontinuation of study drug
- Any treatment-emergent AE leading to death
- Any treatment-emergent AE of special interest as specified in Appendix A
- All deaths

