## 9.5.5 Pregnancy Results

For the Safety Analysis Set, pregnancies and outcomes will be summarized by treatment group for the Treatment Period (placebo-controlled and open-label) and Follow-up Period. Subjects with conception date by sponsor more than 30 days after the last dose of study drug will be included in the summaries for the Follow-up Period.

Listings will be prepared of all pregnancy test results for any subject who ever had a positive pregnancy test at any time point during the study.

Positive pregnancy test results (serum, urine, and both) and a listing of all positive pregnancy test results will be provided.

Pregnancy outcome will be summarized by treatment group. Additionally, a listing of pregnancy information will be provided. Pregnancy outcome includes:

- Number of pregnancies
- Live births
  - Pre-term (extremely pre-term: <28 weeks; very pre-term: 28 -

    < 32 weeks; moderate to late preterm: 32 < 37 weeks)

  - $\circ$  Term (37 < 42 weeks)
  - Post-term ( $\geq$  42 weeks)
- Spontaneous abortion (< 6, 6 13, > 13 weeks gestation)
- Termination of pregnancy

- Ectopic pregnancy
- Still birth
- Congenital anomaly
- Lost to follow-up
- Subjects refused to provide information
- Other
- Ongoing (pregnancy ongoing at end of study)
- Maternal exposure to Elagolix/Study drug (0, > 0 4, > 4 6, > 6 12, > 12 23, > 23 weeks)
- Embryo/Fetal exposure to Elagolix/Study drug assessed by the sponsor (0, > 0 4, > 4 6, > 6 12, > 12 weeks)

Annualized pregnancy rate during treatment will be reported by treatment group. The annualized pregnancy rate will be calculated as

Annualized pregnancy rate = (number of pregnancies/days of exposure to treatment) × 365

In addition, listings of fetal/newborn, infant post-delivery assessments, and infant during 6-12 month follow-up assessment will be provided.

The above information will be summarized primarily based on data collected on the pregnancy case report form. Information not directly obtained from the case report form will use the following definitions.

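### SAP Appendix A finds the spontaneous abortion AESI with a query whose title also covers termination, so elective terminations can fall under that heading

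*SAP*

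**What the plan says.** **AESI definition.** SAP Appendix A pairs each item of safety interest with a method of surveillance. For spontaneous abortion the only method is the "Termination of pregnancy and risk of abortion SMQ". The row gives no narrow or broad scope, preferred-term list, adjudication step or exclusion.

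**AESI reporting.** SAP 9.2.6 states: "Adverse events of special interest will be summarized by SOC and PT and will be based on standardized or company MedDRA queries". It adds the alternative "or based on adjudication results" and sends the reader to Appendix A for the search details. The overview in SAP 9.2.2 has a single AESI line: "Any treatment-emergent AE of special interest as specified in Appendix A".

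**What enters the adverse event data.** Protocol 6.1.1.2 says that "any elective or spontaneous abortion or stillbirth is considered an important medical event". Protocol 6.1.6 applies the same rule to what follows from a pregnancy, where a result "meeting any serious criteria including an elective or spontaneous abortion, stillbirth or congenital anomaly is considered a serious adverse event".

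**Pregnancy outcomes.** SAP 9.5.5 lists spontaneous abortion, in bands of gestational age, and has a separate category "Termination of pregnancy". It draws mainly on the pregnancy case report form. Protocol 6.1.6 already records fetal outcome so that spontaneous and elective abortion are told apart.

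**The concern.** The item names one event, and the search attached to it is titled for a wider class. Spontaneous loss is the outcome that bears on drug safety here: the protocol's rationale for its pregnancy-related entry criteria (5.2.1 and 5.2.2) cites a possible risk of miscarriage through hormone changes. An elective termination is a decision by the woman and does not carry the same information.

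Terminations are plausible in this trial. Women planning a pregnancy within 48 months are excluded and contraception is required, so most pregnancies that occur will be unplanned. They will also be few: Protocol 3.2.3 reports 1 on-treatment pregnancy in the Phase 2b fibroid study and 4 in the Phase 3 studies. With counts that small, one event under the wrong heading is noticeable.

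At stake is whether a reader can take the AESI heading at its word, and whether an AESI total can be matched to the pregnancy outcome table without a case-by-case search.

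**Working it through.** No arithmetic applies. The documents give no count or rate of spontaneous or elective abortion, and the SAP states no figure to reproduce. The check sets the provisions side by side.

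1. **Does the row restrict the query?** No. SAP 9.2.6 points to Appendix A for the search criteria, so no other SAP text narrows it. Adjudication is allowed in general, but Appendix A assigns none to this row.

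2. **Does the appendix narrow other rows?** Yes. The row for other hypoestrogenic events excludes hot flashes, BMD loss and fractures in its label. The obstetrical complications row uses a query whose title excludes abortions and stillbirths. Alopecia is defined by listed terms, and teratogenicity by review of pregnancy outcome. The spontaneous abortion row uses none of these devices.

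3. **Do elective terminations reach the data searched?** Yes. Protocol 6.1.1.2 and 6.1.6 both make them serious events.

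4. **Which of them reach the AESI summaries?** Protocol 8.1.7.2 limits adverse event summaries to treatment-emergent events unless otherwise specified. SAP 9.2.1 ends the window 30 days after last dose for a woman who stops treatment. Under Protocol 6.1.6, study drug stops on a positive serum test, so only terminations within 30 days of the last dose qualify.

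5. **Where would each event appear?** This assumes that the query retrieves what its title names and that all conceptions occur on treatment.

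| Event | Under the spontaneous abortion AESI heading | Preferred term shown | Any-AESI line (9.2.2) | Pregnancy outcome table (9.5.5) |
|---|---|---|---|---|
| Spontaneous loss within 30 days of last dose | Yes | Spontaneous loss | Yes | Spontaneous abortion |
| Elective termination within 30 days | Yes, if retrieved | Termination | Yes, if retrieved | Termination of pregnancy |
| Elective termination after 30 days | No | Not in treatment-emergent tables | No | Termination of pregnancy |

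The second line of the table is the problem. The event sits under a heading that does not describe it. A woman with no other qualifying event also enters the any-AESI count through this row, and display by preferred term does not take her out of that count. The last column is correct throughout.

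**The case against.** The strongest reply is that this is a labelling matter. AESIs are shown by SOC and preferred term, so a termination would appear as a termination. The SAP asks for a single any-AESI line and does not explicitly call for a subtotal per item. Miscarriage is assessed from SAP 9.5.5, which separates the outcomes, rests mainly on the case report form and comes with a listing. Appendix A also uses broad searches elsewhere, such as an osteoporosis/osteopenia query for fractures, which suggests sensitive case-finding with the preferred terms supplying specificity. The query's term list is not in the documents, so retrieval of elective terminations is inferred from its title.

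Most of this stands, and it limits the effect to the item heading, any item total, and the any-AESI line. It does not remove the mismatch. The appendix is titled as a definition, the row's label and search differ, and the protocol supplies the events that fall in the gap.

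A reader might go further and infer that elective terminations will be reported as spontaneous abortions, that miscarriage risk will look inflated, or that two safety outputs will contradict each other. The documents do not support this. The preferred terms stay distinct and the 9.5.5 table does not use the query. The two outputs also differ by design: one covers events in a 30-day window, the other pregnancies followed to their outcome. Their totals could differ even with a perfect filter.

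**Conclusion.** The point holds in limited form. The definition of one AESI is wider, by the title of its only search, than the event it names. Elective terminations in the treatment-emergent window can therefore be classed under spontaneous abortion and counted in the any-AESI line. The AESI item total, if one is produced, may differ from SAP 9.5.5, and no rule is given for reconciling them.

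The conclusion rests on two assumptions: that the query retrieves terms for elective termination, as its title indicates, and that at least one such event falls within 30 days of last dose. The size cannot be stated as a number. The Phase 2b and Phase 3 pregnancy counts in Protocol 3.2.3 come with no split into spontaneous and elective outcomes, so any percentage would be invented.

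This is a modest correction to a mis-specified definition, worth making because it is cheap. It gives no ground for doubting the assessment of miscarriage in SAP 9.5.5.

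**What to change.** Change the one row in SAP Appendix A in either of two ways.

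- **Restrict it.** Keep the label, limit the search to listed preferred terms for spontaneous pregnancy loss, and check the result against the case report form outcome in SAP 9.5.5. The check should allow for the 30-day window, since losses after it appear only in 9.5.5.
- **Rename it.** Give the row a label that matches the query, and report spontaneous loss and elective termination as separate sub-rows. Elective terminations would then still count in the any-AESI line, and a footnote to the overview in SAP 9.2.2 should say so.

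The cost is one row of wording and a term list or grouping in the programming. No new data are needed, because the protocol already collects the distinction between spontaneous and elective abortion.
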